## 7.0 Demographics, Baseline Characteristics, Medical History, and Previous/Concomitant Medications

### 7.1 Demographic and Baseline Characteristics

Demographic data and baseline characteristics are reported for the last non-missing observation before the first dose of study medication in the preceding RCT Study 1311.5. Demographic data and baseline characteristics are not re-assessed before the start of Study M16-244.

Demographic and baseline characteristics will be summarized for the Safety Analysis Set of Study M16-244 for the "All ABBV-066 150 mg q12wks with optional wk4 dose" treatment group. Summaries of baseline characteristics will be presented for the Baseline of Study 1311.5.

The number of observations, mean, standard deviation, median, minimum, Q1, Q3 and maximum will be summarized for continuous variables. Categorical or discrete variables will be summarized via frequencies and percentages. The summary statistic will be computed for the analysis treatment group defined in Section 5.1. No statistical test will be performed.

#### Main Demographic and Baseline Characteristics

- Sex (male/female)
- Ethnicity (Hispanic or Latino, Other)
- Age (years), defined as the number of years from date of birth to date of first drug
- Age Categories (< 65,  $\geq$  65)
- Race (American Indian or Alaska Native, Asian, Black or African American, Native Hawaiian or other Pacific Islander, White)
- Ethnicity (Hispanic or Latino, Other)
- Body Weight (kg)
- Body Weight Categories (< 100 kg,  $\geq$  100 kg)

- Height (cm)
- Body Mass Index (BMI) (kg/m^2)
- Body Mass Index (BMI) Category (kg/m^2) (BMI < 30 vs BMI ≥ 30)

### **PsA Medical History and Disease Characteristics at Baseline**

- Categorical:
  - MDA (Minimal Disease Activity) for PsA
  - sPGA (Static Physician Global Assessment) assessed in subjects with ≥ 3% BSA of psoriatic plaques
  - Presence of Dactylitis (yes/no)
  - Presence of Enthesitis based on LEI (yes/no)
  - Presence of Enthesitis based on SPARCC (yes/no)
  - Presence of nail psoriasis (yes/no)
  - Body Surface Area (BSA) of psoriatic plaques: ≥ 3% vs < 3%
  - Prior exposure to TNF antagonists (TNFi's; Experienced versus Naive)
  - Concurrent exposure to Methotrexate (Concurrent use versus Non-concurrent use)
  - Presence of inflammatory spondylitis (yes/no)
  - Duration of PsA Categories (≤ 5, [5, 10], > 10)
  - Rheumatoid Factor (RF) status: Positive (≥ 15) or Negative (< 15)
- Continuous
  - PASI (Psoriasis Area and Severity Index) assessed in subjects with ≥ 3% BSA of psoriatic plaques
  - DAS28 (Disease Activity Score in 28 joints) – hsCRP
  - Dactylitis count in subjects with dactylitis at baseline 0 – 20
  - Leeds Dactylitis Index (LDI) in subjects with dactylitis at baseline
  - Leeds Enthesitis Index (LEI) in subjects with enthesitis (based on LEI) at baseline (yes/no) 0 – 6
  - Duration since diagnosis of PsA in years

- CASPAR classification criteria total score
- SPARCC (Spondyloarthritis Research Consortium of Canada) Enthesitis Index in subjects with enthesitis (based on SPARCC) at baseline (yes/no) 0 – 16
- mNAPSI (Modified Nail Psoriasis Severity Index) assessed in subjects with nail psoriasis at baseline 0 – 130

### **ACR and/or DAS Components at Baseline**

- SJC (Swollen Joint Count(s) 66) 0 – 66
- TJC (Tender Joint Count(s) 68) 0 – 68
- SJC (Swollen Joint Count(s) 28) 0 – 28
- TJC (Tender Joint Count(s) 28) 0 – 28
- Patient's assessment of pain on VAS 0 – 100
- Patient's global assessment of the disease on VAS 0 – 100
- Physician's global assessment of the disease on VAS 0 – 100
- HAQ-DI (Health Assessment Questionnaire-Disability Index) 0 – 3
- High sensitivity C-Reactive Protein (hsCRP) mg/L

### **Patient Report Outcomes at Baseline**

- SF-36v2 (Short Form-36 Health Survey)
- FACIT-FATIGUE (Functional Assessment of Chronic Illness Therapy-Fatigue) 0 to 52
- BASDAI (Bath AS Disease Activity Index) (in subjects with baseline inflammatory spondylitis) 0 to 10

### **Imaging Characteristics at Baseline**

- mTSS (Modified Total Sharp Score) 0 – 528
  - Total Erosion Score 0 – 320
  - Joint Space Narrowing Score 0 – 208

## Clinical Tests at Screening

- Tuberculin PPD skin test (Negative/Positive/Undetermined), QuantiFERON TB Gold test,
- Hepatitis Testing
- Pregnancy test (Negative/Positive/Not Done/NA)

## General Use

- Smoking status (Never-smoked, Ex-smoker, Currently smokes)
- Alcohol status (Non-drinker, drinks – no interference, drinks – possible interference)

### **7.2 Medical History**

Medical history other than psoriatic arthritis or cardiovascular diseases will be summarized using body systems and condition/diagnosis as captured on the eCRF. The body systems will be presented in alphabetical order and the conditions/diagnoses will be presented in alphabetical order within each body system. The number and percentage of subjects with a particular condition/diagnosis will be summarized for each treatment arm. Subjects reporting more than one condition/diagnosis within a body system will be counted only once for that body system.

### **7.3 Prior Treatment and Concomitant Medications**

Prior and concomitant medications will be summarized. A prior medication is defined as any medication taken prior to the first dose of study drug in Study 1311.5. A concomitant medication is defined as any medication that started prior to the first dose of study drug in Study 1311.5 and continued to be taken after the first dose of study drug or any medication that started after the first dose of study drug, until 140 days (20 weeks) after the last dose of study drug. The number and percentage of subjects who had taken medications will be summarized by generic drug name assigned by the World Health

Organization (WHO) Drug Dictionary for both prior and concomitant medications. The following medication will be summarized:

- Prior systemic corticosteroid
- Prior MTX
- Prior csDMARDs other than MTX
- Prior biologic DMARDs
- Prior NSAIDS
- Concomitant systemic corticosteroid
- Concomitant MTX
- Concomitant csDMARDs other than MTX
- Concomitant NSAIDS

Concomitant biologic DMARDs and csDMARDs other than MTX and on or before Week 16 in Study 1311.5 are protocol violations.

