5.2.3.3 Prohibited Therapy

Use of the following therapies is prohibited from administration of the first dose of study drug in Study 1311.5 throughout the duration of Study M16-244, including any gap between these two studies:

- Investigational products not otherwise described below

- anti-IL-12/23, and anti-IL-17 agents, including ustekinumab and secukinumab
- Cell-depleting therapies including but not limited to anti-CD20 (e.g., rituximab), investigational agents (e.g., CAMPATH, anti-CD4, anti-CD5, anti-CD3, anti-CD19)
- TNF inhibitors
- JAK inhibitor, Apremilast and leflunomide
- Intra-articular injections (including steroids)
- Intramuscular or intravenous corticosteroid treatment
- Topical PsO treatments such as retinoids, Vitamin A analogs, anthralin and steroids except as permitted in Section 5.2.3.2: Concomitant Therapy
- Oral or injectable PsO medications (not biologicals) including retinoids and fumarates, or any other drugs known to possibly benefit PsO
- Photochemotherapy (e.g., PUVA)
- Any drug known to interfere with or to aggravate PsO including but not limited to lithium and interferons
- Phototherapy (e.g., UVA, UVB)
- Low and high potency opioid analgesics (e.g., methadone, hydromorphone, morphine)
- Live or attenuated vaccines

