a. For subjects rolling over from Study 1311.5 to the OLE (Study M16-244) with ≤ 4 day delay, these procedures do not need to be repeated. Results assessed at the Week 24 visit of Study 1311.5 will serve as V1 (Week 0) visit results for Study M16-244. Subjects initiating the OLE with a delay of > 4 days and ≤ 8 weeks from completion of Study 1311.5 Week 24 visit will need to complete all activities for V1. If a subject enrolls into the OLE (Study M16-244), participation in Study 1311.5 is completed and the early completion of the Study 1311.5 is documented (EOS). All procedures of Study 1311.5 trial at Week 24 should be completed prior to the start of the Study M16-244 trial.

b. To be completed prior to initiation of Study M16-244 procedures.

c. Transcribe medical history from Study 1311.5 and record any updates.

d. Subject to complete PROs in the order listed, before any other visit assessments or treatments and, if possible, before any interaction with the investigator or other members of the study team.

- e. A symptom directed physical exam should be performed when necessary and if needed for physician assessments/questionnaires. Complete physical examination will include vital sign assessment and general appearance as well as evaluation of all organ systems. Targeted physical examination will include vital sign assessment and evaluation of organ systems associated with AE(s) symptoms or laboratory abnormalities. Clinically relevant abnormal findings will be reported as baseline conditions or AEs.
- f. For subjects rolling over from Study 1311.5 to the OLE without any delay, concomitant medication ending prior to first dose in Study M16-244 will be recorded in preceding Study 1311.5. Medications ongoing from preceding Study 1311.5 after first dose in Study M16-244 will be recorded in Study M16-244.
- g. For subjects rolling over from Study 1311.5 to the OLE Adverse Events ending prior to completion of Study M16-244 ICF will be recorded in preceding Study 1311.5.
- h. Complete clinical assessment prior to completing Study M16-244 ICF will be recorded in the eCRFs of Study M16-244.
- i. Subjects who prematurely discontinue from the trial will not be required to collect x-rays at each designated time point, unless they received a dose within the 16 weeks prior to the scheduled time point.

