## 10. Safety Subgroup Analysis

The following subgroup analyses will be performed to evaluate the safety in the primary endpoint across demographic data, baseline disease characteristics for PsA.

Subgroup Factor	Categories
Age	< 55 years, ≥ 55 years
Sex	Male or Female
Race	White or Others
Prior TNFi use	Naïve or experienced
Concurrent MTX use	Yes or no

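### SAP 7.3 dates concomitant medication only from the first Study 1311.5 dose, and its DMARD violation sentence stops at feeder Week 16, in conflict with protocol 5.2.3.3 and SAP 7.4

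*SAP*

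**What the plan says.** SAP 7.3 gives two definitions. The first is: "A prior medication is defined as any medication taken prior to the first dose of study drug in Study 1311.5". The second begins "A concomitant medication is defined as any medication that started prior to the first dose of study drug in Study 1311.5" and was kept up after the first dose. It then adds any drug begun after the first dose, "until 140 days (20 weeks) after the last dose of study drug". Within the second definition, only the first mention of a first dose names a study.

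The section summarizes both groups by generic drug name and lists class rows, including one for concomitant csDMARDs other than MTX. It closes with the sentence "Concomitant biologic DMARDs and csDMARDs other than MTX and on or before Week 16 in Study 1311.5 are protocol violations".

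Protocol 5.2.3.3 says that its listed therapies are "prohibited from administration of the first dose of study drug in Study 1311.5 throughout the duration of Study M16-244, including any gap" between the two studies. The list includes TNF inhibitors, anti-IL-12/23 and anti-IL-17 agents, cell-depleting therapies, and "JAK inhibitor, Apremilast and leflunomide".

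SAP 7.4 tabulates four kinds of deviation. One is receipt of a barred concomitant treatment, with neither drugs nor a period named. Another is entry without meeting the eligibility criteria.

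On data capture, protocol 5.2.3.2 has M16-244 record medication received since feeder Week 24. Footnote f of protocol Appendix C covers subjects who roll over without delay. For them, drugs that ended before the first extension dose stay in the feeder records, while "Medications ongoing from preceding Study 1311.5 after first dose in Study M16-244 will be recorded in Study M16-244".

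**The concern.** M16-244 has a single arm. A reader of its safety and efficacy tables has no control group to absorb the effect of other antirheumatic drugs, so the medication summary should show what subjects took during the extension. A definition that starts at the first feeder dose mixes two studies in that summary.

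The violation sentence is a separate problem. It is the only drug-class rule for violations in the SAP, and its stated period ends before the extension begins. A programmer who follows 7.3, one who follows 7.4, and one who works from the protocol list could each produce a different count of subjects with prohibited DMARD use.

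**Working it through.** **The plan's own figure.** SAP 7.3 equates 140 days with 20 weeks: 20 × 7 = 140, which reproduces.

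**Inputs** (nominal visit timing, Week 36 dose taken):
- Feeder, first dose to Week 24 visit: 24 × 7 = 168 days.
- Gap before M16-244: 0 to 8 weeks, that is 0 to 56 days (protocol 5.1).
- Extension, first to last scheduled dose at Week 36: 36 × 7 = 252 days (protocol 5.1).
- Tail after the last dose: 140 days (SAP 7.3).
- Stated period of the violation sentence: 16 × 7 = 112 days from the first feeder dose.

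**Concomitant window**
- Extension part: 252 + 140 = 392 days.
- No gap: 168 + 392 = 560 days. Share before the first extension dose: 168/560 = 30.0%.
- 8-week gap: 168 + 56 = 224 days before the extension, and 224 + 392 = 616 days in all. Share: 224/616 = 36.4%.
- Anchored at the first M16-244 dose, the window is 392 days in both cases.

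**Violation sentence against the same window**
- Covered: 112/560 = 20.0% (no gap) or 112/616 = 18.2% (8-week gap).
- Not covered: 560 − 112 = 448 days (80.0%) or 616 − 112 = 504 days (81.8%). This includes all 392 extension days.

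**Applying the definitions**
- A drug stopped at feeder Week 10 meets the concomitant definition on its natural reading, although it was never taken in M16-244. It reaches the table only if feeder medication records are used.
- A drug taken and stopped in the gap by a delayed entrant also meets the definition. Footnote f returns ended drugs to the feeder only for rollover without delay, and protocol 5.2.3.2 asks for medication since feeder Week 24. This record can therefore sit in the M16-244 eCRF, and no pooling is needed.
- Suppose instead that the later mentions of a first dose mean the M16-244 dose. A drug started during the feeder and continued into the extension is then neither prior nor concomitant.

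Neither reading isolates therapy taken during M16-244.

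**Applying the violation rules to leflunomide**

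| Start of use | SAP 7.3 sentence | Protocol 5.2.3.3 | SAP 7.4 |
|---|---|---|---|
| Feeder Week 18 | outside its period | prohibited | counted, also through exclusion criterion 9 as an entry failure |
| Extension Week 10 | outside its period | prohibited | counted as barred treatment |

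Protocol 3.1 names leflunomide as a traditional DMARD alongside MTX, so it falls in the class that the 7.3 sentence addresses.

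**The case against.** **Flagging.** A reader might infer that prohibited DMARD use in the extension goes unflagged in the SAP. It does not: SAP 7.4 has no Week 16 limit, and both leflunomide examples are caught there. The 7.3 sentence calls certain use a violation; it does not say that later use is not one. This part of the objection stands. What remains is an inconsistent rule.

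**Grammar.** The sentence is ungrammatical. The Week 16 limit may attach only to csDMARDs other than MTX, leaving biologics a violation at any time. That is a fair reading, and the leflunomide conflict persists under it. Leflunomide is also the only csDMARD other than MTX that protocol 5.2.3.3 names. Others could enter only through its general wording.

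**Biologics.** The class list has a row for prior biologic DMARDs and none for concomitant ones. A reader might infer that concomitant biologics appear in no table. The generic-name summary in 7.3 would show them, so at most a class row is absent.

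**MTX subgroup.** A reader might infer that the safety subgroup "Concurrent MTX use" is wrongly defined. SAP 11.2.1 places it among baseline characteristics, and SAP 7.1 lists methotrexate exposure at the feeder baseline. Subgrouping by baseline status is conventional, and a different date would be a preference.

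**Two-study window.** SAP 11.2 reports adverse events for M16-244 alone and for both studies combined, and exposure-adjusted rates use only the combined data. A feeder anchor suits the combined analysis. It does not supply the extension-only summary that the M16-244 tables need.

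**Pooling.** Most of the mixing depends on feeder records being used. Protocol 10.1 permits data sharing but does not require it for this table. This limits the size of the problem, apart from drugs stopped in the gap.

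**Conclusion.** The point holds in two parts. SAP 7.3 has no M16-244 anchor, so drugs stopped in the feeder or the gap can be reported as concomitant when those records are included, and extension therapy is not shown on its own. Its violation sentence, at least for csDMARDs other than MTX, conflicts with protocol 5.2.3.3 and with SAP 7.4, and the three must be reconciled.

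The day counts assume nominal timing, a Week 36 dose and a gap of 0 to 8 weeks. The 30.0% to 36.4% is a share of calendar days. It does not estimate how many drugs or subjects would be misclassified, and the documents give no basis for such an estimate. A drug that runs from the feeder into the extension is classified the same way under the natural reading and under an M16-244 anchor.

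The affected tables are descriptive. Efficacy is summarized as observed (SAP 6.5), so no endpoint value turns on these definitions. What is at stake is the accuracy of the background-therapy summary and a single, reproducible violation count.

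**What to change.** In SAP 7.3:

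1. For M16-244 summaries, define concomitant medication as any drug taken on or after the first M16-244 dose through 140 days after the last dose, whenever it was started. Show the feeder period, or the combined window, in a separate summary to match the combined safety analysis.
2. Replace the Week 16 sentence with a reference to the drugs and period in protocol 5.2.3.3, and have SAP 7.4 use the same reference, so that 7.3, 7.4 and the protocol give one violation count.

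The cost is SAP wording plus a date filter on medication data already collected. No new data are needed, and the protocol's list of prohibited therapies is left as it is. The violation count taken from 7.3 may rise.

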#### **7.4 Protocol Deviation**

Number and percentage of subjects who reported at least one of the following protocol deviation categories will be provided.

- Subject entered into the study even though she/he did not satisfy entry criteria
- Subject who received wrong treatment or incorrect dose
- Subject who received excluded or prohibited concomitant treatment
- Subject who developed withdrawal criteria during the study and was not withdrawn

#### **8.0 Subject Disposition**

The number of subjects will be tabulated by country, investigator site and overall for the Safety Analysis Set. The number of subjects for each of the following categories will be summarized, for overall and for each treatment group in the Safety Analysis Set.

- Number of subjects that took at least one dose of study drug
- Number of subjects who completed Week 36 dose
- Number of subjects who prematurely discontinued from the study before Week 36 dose due to other reasons.

In addition, the reasons for premature discontinuation (primary reason and all reasons) from the trial and/or from the medication collected from CRF by the following categories will be summarized with frequencies and percentages. Subjects with multiple reasons for premature discontinuation will be counted once in the calculation of the number and percentage of total discontinuations ("Premature Discontinuation").

- Adverse event
- Protocol violation
- Lost to follow-up,
- Withdraw by subject,
- Others.

## **9.0 Study Drug Exposure and Compliance**

A summary of study drug duration will be provided for the Safety Analysis Set.

Study drug duration (days) will be summarized with the number of subjects, mean, standard deviation, minimum, median and maximum for each treatment arm. It will also be summarized in 4-week intervals with frequencies and percentages for the number of subjects receiving study drug doses in each interval. In addition cumulative duration of risankizumab (including total subject years) will be summarized.

The study drug duration will be calculated as follows:

Duration = date of last injection – date of first injection + 84 day

Total drug duration across Study 1311.5 (feeder) and Study M16-244 (OLE) will be calculated as follows:

Duration over both studies = date of last injection in Study M16-244 – date of first injection in Study 1311.5 + 84 day – MAX(0, date of first injection in Study M16-244 – date of last injection in Study 1311.5 – 84)

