## 5.0 Analysis Sets

### 5.1 Definition for Analysis Sets

#### Safety Analysis Set

The Safety Analysis Set consists of all subjects who have received at least one dose of study medication in Study M16-244. All efficacy and safety analyses will be based on the Safety Analysis Set.

All efficacy and safety analyses will be summarized for "All ABBV-066 150 mg q12wks with optional wk4 dose" group, which includes all subjects who received at least one dose of ABBV-066 150 mg every 12 weeks in Study M16-244 (with an optional additional dose at Week 4 for subjects with < 20% improvement in tender joint count (TJC) or swollen joint count (SJC)), regardless of what treatment group they were randomized to in Study 1311.5.

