#### **11.2.1 Treatment-Emergent Adverse Events**

All adverse events occurring between start of treatment and end of the residual effect period (REP) will be considered 'treatment emergent.' The REP is defined as 20 weeks (140 days) after the last trial medication application and will include adverse events reported through EOS visit. Adverse events that start before first drug intake and deteriorate under treatment will also be considered as 'treatment-emergent.'

Events where the onset date is the same as the study drug start date are assumed to be treatment emergent, unless the study drug start time and the adverse event start time are

collected and the adverse event start time is prior to the study drug start time. If an incomplete onset date is collected for an adverse event, the event will be assumed to be treatment-emergent unless there is other evidence that confirms that the event is not treatment-emergent (e.g., the event end date is prior to the study drug start date).

Adverse events that occur outside of 140 days from last dose in Study 1311.5 but before first dose in Study M16-244 will not be considered treatment emergent.

The number and percent of subjects experiencing treatment-emergent TEAEs will be tabulated using the Medical Dictionary for Drug Regulatory Activities (MedDRA®) version 20.0 by system organ class (SOC) and preferred term (PT).

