#### 5. **TEAEs by Preferred Term in Descending Frequency**

TEAEs, SAEs, and TEAEs leading to discontinuation of study drug will be summarized by prior and current treatment group in decreasing order of frequency of MedDRA PT in the total risankizumab doses, including AEs occurring after the first dose in Study M16-244 for subjects who received Placebo in Study 1311.5, as well as the highest dose arm from Study 1311.5. The most frequent TEAEs, SAEs and TEAEs leading to discontinuation of study drug can be identified from this summary.

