#### 9. Adverse Event per 100 Patient Years of Exposure in Study 1311.5 and Study M16-244

The treatment-emergent adverse events occurring during Study 1311.5 and Study M16-244 will be presented by event rate per 100 patient year. These will be

---

presented for any TEAEs, serious adverse events, AE of special interest in addition to MACE events.

AEs per 100 patient years of exposure is defined as the number of AEs divided by the total exposure in 100 patient years. Note that one event per preferred term per day per subject will be counted in the calculation of the number of AEs (i.e., a preferred term will not be counted twice on the same day for the same subject). See the calculation method below.

$$100 \times \frac{\text{Number of TEAEs}}{\text{Total Patient Years}}$$

where total patient years is defined as the sum of the study drug exposure (defined in Section 9.0) of all subjects normalized by 365.25, and rounded to one decimal place.

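### Read literally, the pooled per-100-patient-year rates mix placebo and risankizumab time and events for subjects who had placebo in Study 1311.5

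*SAP*

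**What the plan says.** **Exposure (SAP 9.0).** Two durations are defined. The OLE-only one is last minus first injection plus 84 days. The two-study one is "Duration over both studies = date of last injection in Study M16-244 – date of first injection in Study 1311.5 + 84 day", from which only one quantity is subtracted: "MAX(0, date of first injection in Study M16-244 – date of last injection in Study 1311.5 – 84". No term depends on the arm in Study 1311.5. Ahead of both formulas the section announces a further summary, without saying which formula it uses: "In addition cumulative duration of risankizumab (including total subject years) will be summarized".

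**Events (SAP 11.2 and 11.2.1).** The rule is "All adverse events occurring between start of treatment and end of the residual effect period (REP) will be considered 'treatment emergent". Events that fall between the studies are dropped only if they occur more than 140 days after the last Study 1311.5 dose, whatever that dose was. Per-100-patient-year analyses are to use the combined data of the two studies and nothing else.

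**Rate (SAP 11.2.1, item 9).** The numerator is treatment-emergent events from both studies. The denominator is described thus: "where total patient years is defined as the sum of the study drug exposure (defined in Section 9.0) of all subjects normalized by 365.25".

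**Who is included.** SAP 5.1 forms one group of all subjects dosed in M16-244, "regardless of what treatment group they were randomized to in Study 1311.5". SAP 11.3 has a separate laboratory summary for prior-placebo subjects, so such subjects are in the set. SAP 11.2.1, item 5 (preferred terms in descending frequency) describes its risankizumab total as "including AEs occurring after the first dose in Study M16-244 for subjects who received Placebo in Study 1311.5".

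**The concern.** For a subject randomised to placebo in Study 1311.5, the first injection in that study is not risankizumab. The two-study formula still starts there, and the event definition starts at the same point. Placebo time then enters the denominator of the item 9 rates, and placebo-period events enter the numerator. The result is a weighted mixture of a placebo rate and a risankizumab rate.

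The primary objective is the safety and tolerability of risankizumab, and these are the only exposure-adjusted rates in the plan. They are also the figures most likely to be set beside rates from other risankizumab studies. If the cumulative risankizumab duration uses the same formula, it is overstated as well.

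**Working it through.** The documents state no exposure total or rate, so there is no figure to reproduce. The check evaluates the SAP formula directly.

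**Inputs**
- OLE dosing at Weeks 0, 12, 24 and 36 (Protocol 5.1): a completer has 36 × 7 = 252 days from first to last dose.
- OLE entry on the day of the Study 1311.5 Week 24 visit or up to 8 weeks later (Protocol 5.1). With the first feeder injection at Week 0 (assumed), the time *T* from first feeder injection to first OLE injection is about 168 to 224 days.
- Day *L* of the last feeder injection: not given; values of 0, 84 and 112 are tried.
- Prior-placebo share *f*: not given; 10% to 33% is tried.

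**Per subject**

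Two-study duration = *T* + 252 + 84 − max(0, *T* − *L* − 84). Risankizumab-only duration of a prior-placebo completer = 252 + 84 = 336 days.

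| Case | Two-study days | Days before first risankizumab dose | Share |
|---|---|---|---|
| *T* = 168, *L* = 84 or 112 | 168 + 252 + 84 − 0 = 504 | 168 | 33.3% |
| *T* = 224, *L* = 112 | 224 + 252 + 84 − 28 = 532 | 196 | 36.8% |
| *T* = 168, *L* = 0 | 168 + 252 + 84 − 84 = 420 | 84 | 20.0% |
| One OLE dose only, *T* = 168, *L* = 112 | 168 + 0 + 84 − 0 = 252 | 168 | 66.7% |

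**Pooled**

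Assume that all subjects complete with 504 days each. The placebo share of patient-years is then *s* = *f* × 168/504 = *f*/3. With the enrolment ceiling of 180, total time is 180 × 504/365.25 = 248.4 patient-years.

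| Assumed *f* | Placebo patient-years | Risankizumab patient-years | *s* |
|---|---|---|---|
| 10% | 8.3 | 240.1 | 3.3% |
| 20% | 16.6 | 231.8 | 6.7% |
| 33% | 27.3 | 221.1 | 11.0% |

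The upper value may be generous. Protocol 5.6.4 describes 150 mg at more than one frequency plus a single 75 mg dose, so at least three active regimens. Under equal allocation (assumed) placebo would be at most 25%, giving *s* = 8.3%.

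**Effect on a rate**

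Pooled rate = (1 − *s*) × risankizumab rate + *s* × placebo rate. With *r* the placebo-to-risankizumab rate ratio, the relative error is *s*(*r* − 1).
- *f* = 20%: −3.3% at *r* = 0.5, zero at *r* = 1, +6.7% at *r* = 2.
- *f* = 33%: −5.5% at *r* = 0.5, +11.0% at *r* = 2.
- An event that never occurs on placebo (*r* = 0) is understated by *s* itself: 3.3% to 11.0% over the range of *f*.

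**The case against.** **The gap is an omission.** The SAP nowhere says that placebo counts as drug, and item 5 shows that the authors knew the right rule. A reader might go further and call the SAP self-contradictory. The text does not support that: item 5 governs a different table, and its rule was simply not carried into Section 9.0 or item 9. Even so, a programmer who follows those two sections as written will include the placebo period.

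**Item 9 does not name a duration.** Section 9.0 defines two. This stands. The two-study duration is the likely one because SAP 11.2 restricts these rates to combined data. The OLE-only duration would be no better: events from two studies would be divided by one study's time, 336 instead of 504 days for the completer above, and at a constant event rate the result would be inflated by 504/336 − 1 = 50%.

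**Columns might be split by prior arm.** Items 2, 5 and 6 use prior and current treatment groups; item 9 is silent. A split alone would not cure the problem. In a prior-placebo column, 20% to 37% of a completer's credited time would precede risankizumab.

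**The main safety results are intact.** This also stands. A reader might infer that the primary safety analysis is compromised. SAP 11.2 plans event frequencies from M16-244 alone, where every subject is on risankizumab, and Protocol 8.1.6 asks for incidences, tabulations and listings, not exposure-adjusted rates.

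**Placebo enters both numerator and denominator.** Correct, so the direction of the error is not fixed. A reader might infer that the rates systematically understate risk. That holds only for events more frequent on risankizumab than on placebo.

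**Conclusion.** The point holds as a should-fix. With the two-study duration as denominator, the plan's only per-100-patient-year rates are mixed placebo and risankizumab rates. The error is too low, too high or nil according to whether the event is more, less or equally frequent on risankizumab than on placebo.

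For one prior-placebo completer, with same-day rollover and a last feeder injection at Week 12 or later, 168 of 504 credited days are placebo. That 50% excess over 336 days should not be read as the pooled effect. In the pool, placebo is about 3% to 11% of patient-years, if all subjects complete and the prior-placebo share is 10% to 33%. Full completion is a simplification, since Protocol 5.4.1 requires persistent non-responders to be withdrawn.

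It is also tempting to say that the cumulative risankizumab duration is overstated. The SAP does not tie that summary to either formula, so this is conditional on the two-study formula being used for it.

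**What to change.** In SAP 9.0 and in 11.2.1, item 9:

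1. State that item 9 uses the two-study duration.
2. For subjects randomised to placebo in Study 1311.5, start both exposure and treatment-emergent event counting at the first M16-244 dose. Their duration is then last minus first M16-244 injection plus 84 days. Keep the two-study clock for subjects randomised to risankizumab.
3. If the placebo period is reported, give its time and events a separate column.
4. Apply the same start date to the cumulative risankizumab duration, or say which formula that summary uses.

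The cost is one SAP sentence, a conditional start date in the exposure and event derivations, and fewer pooled patient-years. In the illustration above, 248.4 becomes 240.1, 231.8 or 221.1 at an assumed share of 10%, 20% or 33%. The time removed was never on risankizumab. Item 9 plans no confidence intervals, so no planned interval changes.

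One limit remains. The change deals with the placebo arm only. Protocol 5.6.4 mentions a single-dose 75 mg regimen in Study 1311.5, and the documents do not say whether those subjects later received dummy injections. If they did, the handling of that time should be stated too.
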